6. TREATMENTS

The following is a list of the study treatment abbreviations that will be used in the TFLs.

Study Treatment Name	Treatment order in TFL
15 U LY900014 SC	1
15 U Humalog SC	2

7. SAMPLE SIZE JUSTIFICATION

Up to 40 patients will be randomized in order that approximately 28 patients complete the study. Twenty-eight completing patients will provide approximately 92% power to demonstrate a 40% increase in the insulin lispro area under the concentration versus time curve (AUC) from time zero to 30 minutes (AUC[0-30min]) between LY900014 and Humalog. Testing will be done at an alpha level of 0.05 with a 2-sided confidence interval (CI). The variability was estimated by analyzing a Lilly internal study that showed a log-scale standard deviation (SD) of within-patient difference in AUC(0-30min) of 0.5. Analysis of internal data showed a log-scale SD of within-patient difference in time to early half-maximal serum concentration (early 50% t_{max}) of 0.5, which provides approximately 95% power to show a 30% reduction in early 50% t_{max} , testing with an alpha level of 0.05 and a 2-sided CI.

In addition, the study is adequately powered to evaluate the GD parameters. There is approximately 71% power to detect a 20% decrease in both time to onset of insulin action (T_{onset}) and time to early half-maximal GIR before time to maximum glucose infusion rate (TR_{max}) (early 50% TR_{max}), and approximately 81% power to detect at least a 40% increase in total amount of glucose infused over 30 minutes ($G_{tot}[0-30min]$) and total amount of glucose infused over 1 hour ($G_{tot}[0-1h]$). In estimations, the log-scale SD of within-patient difference was used with 0.45 for T_{onset} and early 50% TR_{max} , and 0.6 for $G_{tot}(0-30min)$ and $G_{tot}(0-1h)$.

Patients who discontinue from the study prior to completion of both treatment periods with evaluable primary outcome data can be replaced to ensure that enough patients may complete the study. The replacement patient will adopt the original patient's randomized treatment sequence.

8. DEFINITION OF ANALYSIS POPULATIONS

The "Safety" population will consist of all patients who received at least one dose of study drug.

The primary statistical analyses for PK will be conducted on those patients who receive at least 1 dose of study drug and have measurable insulin lispro concentrations.

The primary statistical analysis for GD will be conducted on those patients who receive at least 1 dose of study drug and who complete at least 1 clamp procedure.

Supportive analyses will also be performed on the key PK and GD parameters for the patients who complete all treatment periods with evaluable data.

All protocol deviations that occur during the study will be considered for their severity/impact and will be taken into consideration when patients are assigned to analysis populations.

9. STATISTICAL METHODOLOGY

9.1 General

Data listings will be provided for all data that is databased. Summary statistics and statistical analysis will only be presented for data where detailed in this SAP. For continuous data, summary statistics will include the arithmetic mean, arithmetic SD, median, min, max and N; for log-normal data (e.g. the PK parameters: AUCs and maximum observed drug concentration [C_{max}]) the geometric mean and geometric coefficient of variation (CV%) will also be presented. For categorical data, frequency count and percentages will be presented. Data listings will be provided for all patients up to the point of withdrawal, with any patients excluded from the relevant population highlighted. Summary statistics and statistical analyses will generally only be performed for patients included in the relevant analysis population. For the calculation of summary statistics and statistical analysis, unrounded data will be used.

Mean change from baseline is the mean of all individual patients' change from baseline values. Each individual change from baseline will be calculated by subtracting the individual patient's baseline value from the value at the timepoint. The individual patient's change from baseline values will be used to calculate the mean change from baseline using a SAS procedure such as Proc Univariate.

Data analysis will be performed using CCI or greater.

9.2 Demographics and Patient Disposition

Patient disposition will be listed. The demographic variables age, sex, race, ethnicity, country of enrolment, site ID, hip and waist circumference, body weight, height and body mass index will be summarized by age group and listed. In addition, screening HbA1c, fasting blood glucose, fasting C-peptide, previous insulin therapy (basal and prandial) and duration of T1DM will be summarized and listed.

9.3 Pharmacokinetic Assessment

9.3.1 Pharmacokinetic Parameter Estimation

Patients who receive at least 1 dose of study drug and have measurable insulin lispro or treprostimil concentrations will be included in the PK analysis dataset.

The PK analyses will be conducted by Eli Lilly using standard noncompartmental methods of analysis using CCI on a computer that meets or exceeds the minimum system requirements for these programs. The version of any software used for the analysis will be documented and the program will meet the

Lilly requirements of software validation. It is possible that other validated equivalent PK software programs may be utilized if appropriate, warranted, and approved by global PK management.

Free serum insulin lispro concentrations will be used to calculate several PK parameters, including: early 50% t_{max} , time to late half-maximal serum concentration (late 50% t_{max}), C_{max} , time to maximum observed drug concentration (t_{max}), AUC from time zero to the last recorded time, AUC from time zero to 15 minutes, AUC(0-30min), AUC from time zero to 1 hour, AUC from time zero to 10 hours, and AUC from time zero to infinity. Other parameters may be calculated as deemed appropriate. Additional partial AUCs may be computed as necessary. The primary insulin lispro PK parameters for faster insulin lispro absorption analysis are early 50% t_{max} and AUC(0-30min).

Given the predicted low systemic concentrations of treprostinil, the PK analysis of treprostinil from the LY900014 dosing will be conducted using the available data. The primary analysis of the treprostinil concentrations will be focused on assessing time of maximum observed drug concentration (t_{max}) and C_{max} .

Although attempts will be made to adhere to the scheduled collection times, it is recognized that situations arise that may compromise the scheduled times. Parameters will be individually calculated for each patient based on actual collection times and presented using summary statistics.

9.3.2 Pharmacokinetic Statistical Inference

Log-transformed C_{max} and AUC estimates for insulin lispro will be evaluated to estimate least squares (LS) geometric means, ratios of geometric means between LY900014 and Humalog, and their corresponding 95% CIs using the mixed-effects model that includes treatment, sequence, and period as fixed effects and patient within sequence as a random effect.

Example SAS code:

```
proc mixed data=pk;
class patient period treatment sequence ;
model logpk = treatment period sequence / ddfm=kr;
random patient(sequence);
lsmeans treatment;
run;
```

The same model without log transformation will be used for the analysis of the PK time parameters (early 50% t_{max} , late 50% t_{max} , and t_{max}). LS means, treatment differences in LS means, and the corresponding 95% CIs for the treatment differences will be estimated from the model. The treatment ratios and 95% CIs for the ratios will be calculated using Fieller's theorem.

Statistical significance will be achieved when the p-value for a test is less than 0.05.

The analyses described above will also be performed on the population of patients who completed and had evaluable PK data for both study periods.

9.4 Pharmacodynamic Assessment

9.4.1 Glucodynamic Parameter Estimation

Glucodynamic assessments will be calculated by Eli Lilly from the euglycemic clamp procedure, where the GIR over time will be used as a measure of insulin effect. Glucodynamic analyses will be conducted on those patients who complete at least 1 clamp procedure.

A locally weighted scatterplot smoothing (LOESS) function will be applied to all individual GIR versus time profiles in each treatment group and/or period using CCI software version 8.2. The fitted data for each patient will be used to calculate the following GD parameters: maximum GIR (R_{max}), TR_{max} , early 50% TR_{max} , time to half-maximal GIR after TR_{max} (late 50% TR_{max}), T_{onset} , G_{tot} over the duration of the clamp procedure, $G_{tot}(0-1h)$, and $G_{tot}(0-30min)$. The values of these GD parameters will be summarized by treatment group through descriptive statistics. Mean LOESS fits of GIR versus time profiles will be generated. The primary GD parameters for analysis are early 50% TR_{max} , $G_{tot}(0-30min)$, $G_{tot}(0-1h)$, and T_{onset} .

Additional partial glucose AUCs, such as G_{tot} over 2 hours ($G_{tot}[0-2h]$) and G_{tot} from 3 hours to the end of the clamp ($G_{tot}[3h-END]$), G_{tot} from 4 hours to the end of the clamp ($G_{tot}[4h-END]$), may be computed as necessary.

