Clinical Laboratory Tests	X		Up to 2 hours predose in Period 1 only		X	See Appendix 2 , Clinical Laboratory Tests, for details. Samples collected after a fast of at least 8 hours. Additional tests may be performed at the discretion of the investigator.
Pregnancy Test	X	X			X	Female patients only. Serum pregnancy test at screening, and urine pregnancy test at all other time points.

Procedure	Screening	Treatment Periods 1 and 2			Follow-up /ED	Comments
	Within 28 days prior to Day 1	Day -1	Day 1	Day 2	≥14 days after last dose	
FSH	X					Women of non-childbearing potential only.
Urine Drug Screen	X					
Injection-site Local Tolerability Assessments			0, 60, 240 minutes postdose, end of clamp procedure			Assessments at time 0 are immediately following dosing.
VAS Assessment of Injection-site Pain			0, 60, 240 minutes postdose, end of clamp procedure			Assessments at time 0 are immediately following dosing.
PK Sampling for Insulin Lispro			Predose (0), 5, 10, 15, 20, 25, 30, 35, 40, 45, 50, 55, 60, 70, 90, 120, 150, 180, 240, 300, 360, 420, 480, 540, 600 minutes postdose			Sampling times are relative to study drug administration time (0 minutes).
PK Sampling for Treprostinil			15, 30, 60, 120 minutes postdose			Sampling times are relative to study drug administration time (0 minutes).
Euglycemic Clamp			From 0 up to 10 hours postdose			
Blood Glucose Monitoring (Euglycemic Clamp)			X			Every minute during the run-in and for the duration of the euglycemic clamp until up to 10 hours postdose.
Pharmacogenetics Sampling			X			Samples collected predose in Period 1 only.
Immunogenicity Sampling			X		X	Day 1 samples will be collected predose (up to 2 hours prior to dosing) for Period 1 and Period 2. Additional samples may be collected if the investigator considers an AE is possibly immunologically indicated.

Abbreviations: CRU = clinical research unit; ECG = electrocardiogram; ED = early discontinuation; FSH = follicle-stimulating hormone; ICF = informed consent form; PK = pharmacokinetic; VAS = visual analog scale.

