4. Objectives and Endpoints

Table ITRZ.1 shows the objectives and endpoints of the study.

Table ITRZ.1. Objectives and Endpoints

Objectives	Endpoints

Primary
 
To compare the PK of insulin lispro following administration of a single 15-U SC dose of LY900014 to insulin lispro (Humalog) in Japanese patients with T1DM.
	
Early 50% t_{\max} and $AUC_{(0-30\text{min})}$

Secondary
 
 To compare the GD during a euglycemic clamp following administration of a single 15-U SC dose of LY900014 or insulin lispro (Humalog) in Japanese patients with T1DM. To evaluate the safety and tolerability of the proposed commercial formulation of LY900014. 	
 Early 50% TR_{\max}, $Gtot_{(0-30\text{min})}$, $Gtot_{(0-1\text{h})}$, and T_{onset} AES

Abbreviations: AE = adverse event; $AUC_{(0-30\text{min})}$ = area under the concentration versus time curve from time zero to 30 minutes; early 50% t_{\max} = time to early half-maximal serum concentration; early 50% TR_{\max} = time to early half-maximal glucose infusion rate before time to maximum glucose infusion rate; GD = glucodynamic; $Gtot_{(0-1\text{h})}$ = total amount of glucose infused over 1 hour; $Gtot_{(0-30\text{min})}$ = total amount of glucose infused over 30 minutes; PK = pharmacokinetics; SC = subcutaneous; T1DM = type 1 diabetes mellitus; T_{onset} = time to onset of insulin action.

5. Study Design

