9.6.1.1. Euglycemic Clamp Procedure

Patients will participate in 2 euglycemic clamps across 2 treatment periods. After at least 8 hours overnight fast, the euglycemic clamp procedure will be performed for approximately 10 hours following administration of a dose of insulin lispro according to the Schedule of Assessments (Section 2) and as described in Section 5.1.

Approximately 1 to 6 hours before the planned administration of study drug, patients will be connected to the clamp device CCI [REDACTED] for continuous blood glucose monitoring and receive a variable IV infusion of either insulin glulisine or glucose to obtain a

steady blood glucose clamp target of 100 mg/dL ($\pm 20\%$) (5.5 [± 1.1] mmol/L). The target blood glucose level of 100 mg/dL (5.5 mmol/L) $\pm 20\%$ (upper and lower limits included) must be kept at -60 to -30 minutes before trial product administration, followed by the target blood glucose level of 100 mg/dL (5.5 mmol/L) $\pm 10\%$ (upper and lower limits included) within the last 30 minutes prior to trial product administration without any glucose infusion. The IV insulin glulisine infusion (if any) is lowered as much as possible to keep the blood glucose concentrations at the target without having to infuse glucose. The insulin glulisine infusion is tapered off and should be stopped 10 minutes [REDACTED] minutes before trial product administration as measured by CCI [REDACTED], and the onset of study insulin action occurs when blood glucose drops to 5 mg/dL (0.3 mmol/L) from baseline. If there are no stable blood glucose measurements with CCI [REDACTED] in the last minutes before intended dosing, dosing should be postponed and the run-in period will be prolonged. If the target blood glucose level cannot be established before 14:00, the visit will be terminated and the patient may be rescheduled for a new dosing visit 1 to 7 days later. After the onset of action has been reached, a variable IV glucose infusion will be initiated in order to keep blood glucose constant at the target level. The GIR necessary to keep the blood glucose concentration at the target level will be recorded using a validated data capture system at the CRU.

The clamp procedure will continue for up to 10 hours after dose or until after blood glucose concentrations increased to >200 mg/dL (11.1 mmol/L) without any glucose being administered for at least 30 minutes, whichever is earlier.

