10.3.3. Pharmacodynamic Analyses

10.3.3.1. Glucodynamic Parameter Estimation

Glucodynamic assessments will be determined from the euglycemic clamp procedure, where the GIR over time will be used as a measure of insulin effect. Glucodynamic analyses will be conducted on those patients who complete at least 1 clamp procedure.

A locally weighted scatterplot smoothing (LOESS) function will be applied to all individual GIR versus time profiles in each treatment group and/or period using CCI. The fitted data for each patient will be used to calculate the following GD parameters: maximum GIR (R_{max}), TR_{max} , early 50% TR_{max} , time to half-maximal GIR after TR_{max} (late 50% TR_{max}), T_{onset} , G_{tot} over the duration of the clamp procedure, $G_{tot(0-1h)}$, and $G_{tot(0-30min)}$.

The values of these GD parameters will be summarized by treatment group through descriptive statistics. Mean LOESS fits of GIR versus time profiles will be generated. The primary GD parameters for analysis are early 50% TR_{max} , $G_{tot(0-30min)}$, $G_{tot(0-1h)}$, and T_{onset} .

Additional partial glucose AUCs, such as G_{tot} over 2 hours ($G_{tot[0-2h]}$) and G_{tot} from 3 hours to 10 hours ($G_{tot[3-10h]}$), may be computed as necessary.

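### T_onset is defined by a fall in blood glucose but calculated from LOESS-fitted GIR, an indirect marker, with no stated span, threshold or read-off rule

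*SAP*

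**What the plan says.** **Definition.** Table ITRZ.1 (protocol section 4) lists T_onset among the secondary glucodynamic endpoints and expands it only as "T_{onset} = time to onset of insulin action". Protocol 9.6.1.1 says when that onset happens: "the onset of study insulin action occurs when blood glucose drops to 5 mg/dL (0.3 mmol/L) from baseline". I read this as a fall of 5 mg/dL, since a level of 5 mg/dL cannot be squared with a clamp target of 100 mg/dL. The same section adds: "After the onset of action has been reached, a variable IV glucose infusion will be initiated".

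**Calculation.** Protocol 10.3.3.1 smooths GIR only: the LOESS "function will be applied to all individual GIR versus time profiles in each treatment group and/or period". It continues: "The fitted data for each patient will be used to calculate the following GD parameters", and T_onset is in the list that follows. SAP 9.4.1 has the same sentence, "The fitted data for each patient will be used to calculate the following GD parameters: maximum GIR", and the same list, including "T_{onset} , G_{tot} over the duration of the clamp procedure".

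**Data available.** The Schedule of Activities (protocol section 2) has blood glucose read as follows: "Every minute during the run-in and for the duration of the euglycemic clamp until up to 10 hours postdose".

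**Use.** Both documents name T_onset as one of four primary GD parameters. Protocol 10.3.3.2 and SAP 9.4.2 analyse it untransformed, with a p-value for the difference in least-squares means and a Fieller ratio.

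**The concern.** The event is defined on one measurement and the endpoint is computed from another. A fitted GIR curve contains no blood glucose, so the 5 mg/dL criterion cannot be applied to it directly. What the curve can supply is a time at which the fitted rate leaves zero or passes some level. That time depends on three things besides insulin action: the delay between the glucose fall and the start of infusion, the smoothing span, and the level taken as onset. A smoother also spreads the rise back into the minutes before infusion began. It need not shift a fast and a slow onset equally, so the difference and the ratio can change while the glucose-defined onsets stay the same.

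The planned effect is small in absolute terms. A 20% decrease on an assumed reference onset of 25 min is 0.20 × 25 = 5 min, which smoothing can match. There is also a reason to fix the rule in advance: protocol 7.3 leaves the sponsor's study team unblinded, and SAP 9.4.1 has the sponsor calculate the GD parameters.

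**Working it through.** **1. The plan's own figure.** Protocol 10.1 and SAP 7 give about 71% power for a 20% decrease in T_onset, with 28 completers, a log-scale SD of the within-patient difference of 0.45 and two-sided alpha 0.05. The noncentrality is |ln 0.80| / 0.45 × √28 = 0.2231 / 0.45 × 5.2915 = 2.624. With 27 df (critical t 2.052) the noncentral t gives 71.6%; with 26 df (2.056) it gives 71.4%. The figure reproduces. The calculation takes nothing from how T_onset is read, so this point does not alter it.

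**2. The texts side by side.**

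| Item | Protocol 9.6.1.1 | Protocol 10.3.3.1 and SAP 9.4.1 |
|---|---|---|
| Measurement | Blood glucose | LOESS-fitted GIR |
| Event | Fall from baseline | Not stated |
| Order | Before glucose infusion | At or after infusion start, before smoothing |
| Span, threshold, read-off rule | Not applicable | Not stated |

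No sentence exempts T_onset from the fitted-data list or explains how the two sources agree.

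**3. How far the unstated choices matter.** All inputs here are assumptions; the documents give none of them. The GIR is noise-free, one value per minute for 10 h: zero until onset, then a rise to 8 mg/kg/min, then a Gaussian decline (SD 100 min; SDs of 80 and 120 min gave the same readings). The fast profile has onset at 15 min and peak at 110 min; the slow one, 25 and 130 min. The true difference is 10 min and the true ratio 15/25 = 0.60. With u the fraction of the rise completed, the concave rise is 8[1 − (1 − u)²] and the convex rise is 8u². Onset is read as the first minute at which the LOESS fit (no robustness iterations) exceeds 0.05 mg/kg/min.

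| Span | Concave: fast, slow (min) | Diff. | Ratio | Convex: fast, slow (min) | Diff. | Ratio |
|---|---|---|---|---|---|---|
| None | 16, 26 | 10 | 0.62 | 23, 34 | 11 | 0.68 |
| 2% | 14, 24 | 10 | 0.58 | 23, 33 | 10 | 0.70 |
| 5% | 8, 19 | 11 | 0.42 | 21, 32 | 11 | 0.66 |
| 10% | 9, 13 | 4 | 0.69 | 15, 24 | 9 | 0.63 |
| 15% | 10, 14 | 4 | 0.71 | 17, 21 | 4 | 0.81 |
| 20% | 8, 15 | 7 | 0.53 | 21, 24 | 3 | 0.88 |
| 30% | 0, 10 | 10 | 0 | 23, 29 | 6 | 0.79 |

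At a 2% span the fit adds little to the unsmoothed reading. At 5% to 20% the ratio runs from 0.42 to 0.71 (concave) and 0.63 to 0.88 (convex). On the convex curve part of the departure from 0.60 comes from the threshold: the unsmoothed ratio is already 0.68.

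**4. At the planned effect.** A second assumed curve, 8x·exp(1 − x) with x the time since onset divided by the time from onset to peak, had onsets of 20 and 25 min and peaks at 110 and 135 min (true ratio 0.80, difference 5 min). Onset was the last minute before the peak with the fit still at or below 1% of its maximum. A 2% span gave 18 and 23 min (18/23 = 0.78); a 10% span gave 10 and 12 min (10/12 = 0.83, difference 2). With 5% of maximum as the threshold, spans of 2% to 20% gave ratios of 0.75 to 0.81.

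**The case against.** The strongest reply is that the two sources are linked. No glucose is infused in the last 30 minutes before dosing, and the infusion starts once onset is reached. The unsmoothed start of the GIR is therefore a recorded consequence of the defined event. This stands. A reader might infer that T_onset will not measure the defined event at all, or cannot be recovered from infusion data; the documents do not support that. They do, however, specify the fitted curve and not the raw start.

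Second, protocol 9.6.1.1 never uses the label T_onset. The link runs through the shared phrase about onset of insulin action, and text beside the definition is redacted and may hold the baseline rule. The link is thus a reasonable inference, and the absence of a visible baseline is not counted as an error. The redaction does not change what the two estimation sections name as the source.

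Third, the illustration depends on its assumptions. The ratio of 0 needs a 30% span (about 3 h of a 10 h clamp), a concave rise and a threshold of 0.05/8 = 0.6% of the peak; the convex rise never gives it. With a threshold of 1.0 mg/kg/min on the concave curve, spans of 5% to 20% give ratios of 0.63 to 0.69 and differences of 8 to 11 min, against 0.69 and 10 unsmoothed. A well-chosen rule could work. A reader might take the table as evidence of bias in this trial; it is not.

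Fourth, a glucose-based rule has its own weakness. Pre-dose glucose may lie within ±10% of 100 mg/dL, that is 90 to 110 mg/dL, a band wider than the 5 mg/dL fall. A bare first crossing could be drift or noise. This also stands and shapes the fix.

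**Conclusion.** The concern holds in a limited form. Both documents name a source for T_onset that differs from the measurement on which the protocol defines onset, and nothing reconciles them. That is a conflict between stated rules, beyond a missing detail. In the main illustration, spans of 5% to 20% with a low threshold moved a true ratio of 0.60 to anywhere between about 0.4 and 0.9 and a true difference of 10 min to between 3 and 11 min, with the direction depending on curve shape. A narrow span or a higher threshold reduced the movement considerably. These figures rest on assumed noise-free curves, spans and thresholds, so they measure sensitivity and do not predict this trial's result.

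The consequence is confined to one of four secondary GD endpoints. The primary PK endpoints are untouched.

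**What to change.** - In protocol 10.3.3.1 and SAP 9.4.1, remove T_onset from the parameters calculated from fitted GIR.
- Derive it from the minute-by-minute blood glucose record by the fall-from-baseline criterion in protocol 9.6.1.1. State how baseline is computed and how many consecutive readings must meet the criterion. Keep that number small, because the infusion that follows onset brings glucose back towards target.
- Show any GIR-based onset as supportive, under a different name, saying whether it uses raw or fitted data, with what threshold and, if fitted, what span.
- Settle this before the GD parameters are calculated.

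This concerns only the derivation of the endpoint and leaves the clamp procedure as it is. The glucose data are already collected, so the cost is wording in two documents and a small programming change. No power or sample-size figure changes.
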